## **7 Sample Size**

An initial sample size target of 150 participants (up to 190 consented and screened subjects to achieve 75 randomized per treatment group) was identified based on recent clinical trial experience and logistical considerations including the number of clinical centers with appropriate leadership and infrastructure to be considered as state of the art for treating SSc-ILD. Statistical analysis, using a clinical trials simulation approach, was then employed to estimate the power to detect various treatment effects on the primary endpoint with a two-sided Type I error of 5% and an 18-month attrition estimate of 24%.

[figure not shown]
Data from the SLS I and II clinical trials were used to estimate the baseline characteristics of the proposed study population and their response over time to treatment with MMF, including the impact of prior treatment with MMF (occurring prior to study randomization), on the predicted course of lung function changes over time. Note that SLS III will employ essentially the same patient recruiting centers and investigators as those that participated in the prior studies (with some new additions) and that the enrollment criteria have been relatively conserved over time to assure reproducibility. Furthermore, both the control arm and experimental arm of the proposed study will be treated with a course of cytotoxic therapy that is essentially identical to that reported from the SLS I and II studies. For the impact of PFD, safety and tolerability data from the LOTUSS trial and outcome data from studies in which PFD was used to treat IPF were considered informative.

Two outcome scenarios were considered based on the two potential mechanisms of action by which the addition of PFD might improve the response to treatment with MMF alone. Both scenarios assume that the average response pattern to MMF alone (the control arm) would approximate the average response pattern to cytotoxic therapy observed from SLS II. In that study, the overall improvement from baseline in the FVC-% was approximately 3.0% at the 12 month time point and 4.25% at 18

months. Two different response scenarios were then proposed to represent the range of possible responses in patients treated with combined MMF+PFD (the experimental arm).

- **In Scenario 1**, it is assumed that treatment with PFD is associated with an early slowing of the decline in lung function normally observed during the first 3-6 months of cytotoxic therapy and that there is only a small additive effect of PFD to the later improvement in lung function. The collective result is a 2.5% greater response to treatment at 12 months in the experimental versus control arms and this difference between the groups remains the same for the duration of the 18-month study.
- **In Scenario 2**, it is assumed that treatment with PFD is associated with both an early slowing of the decline in lung function and a definite additive effect on the overall improvement in FVC-% that continues throughout the entire treatment period. The collective result is a 3.125% greater response to treatment at 12 months in the experimental versus control arms which continues to slowly increase to a final 3.25% difference between the two groups at 18 months.

**Figure 7.1. Hypothesized Response Trajectories over the 18-Month Double-Blind Treatment Period by Treatment Group with two scenarios considered, all participants naïve to therapy.**

The power to detect a response based on each Scenario was then calculated by carrying out 1,000 clinical trials simulations for each scenario in SAS 9.4, using a linear mixed model with participant-month in the study (3, 6, 9, 12, 15 and 18) as the unit of analysis and the change from baseline in FVC-% as the outcome, with terms for treatment group, baseline FVC-%, month and the interaction of treatment group with month as a fixed covariate and participant as a random effect to account for the correlation of outcomes over time within a participant. (This is a simplification of the model used for the primary analysis of the primary endpoint described above.) We used a compound symmetry variance-covariance structure. The average power is calculated as the number of simulations where the F-test used to test the hypothesis that the mean change from baseline during the double-blind treatment period differs between the two treatment groups is rejected ( $p \leq 0.05$ ) divided by the number of simulations. 95% CIs for power are calculated based on the exact binomial proportion.

**Table 7.1.** Power to detect differences in the response pattern from baseline to 18 months for the primary outcome (change in FVC-%) when comparing the course of change in lung function over time for the MMF+PFD arm and the MMF+Plac arm according to the two proposed outcome scenarios. Results assume a 5% two-sided type I error and are provided for three different sample sizes (N = 75/arm; 70/arm and 65/arm)

Assumptions: 
 
- Drop-out rates, variances and data inter-correlations presented below are derived from SLS I and II data and assumed to be identical for the two defined scenarios
 
- A 5% two-sided type I error is assumed
 
- The difference in the outcome measure between treatment arms (relative difference in the change from baseline in absolute FVC %-predicted) for each scenario was estimated based on the hypothetical response to PFD proposed for each scenario as detailed in Figure 7.5.4.
 
				
Scenario 1 Difference between treatment arms (FVC-%)	Scenario 2 Difference between treatment arms (FVC-%)	Dropout (Cumulative %)	SD Estimate	Assumed Correlations (AR1):
Mo 3: 0.5	Mo 3: 0.75	Mo 3: 6.5%	Mo 3: 4.1	3-mo intervals: 0.866
Mo 6: 1.375	Mo 6: 1.75	Mo 6: 13%	Mo 6: 5.1	6-mo intervals: 0.834
Mo 9: 2.25	Mo 9: 3.0	Mo 9: 17%	Mo 9: 6.2	9-mo intervals: 0.802
Mo 12: 2.5	Mo 12: 3.125	Mo 12: 20%	Mo 12: 6.9	12-mo intervals: 0.790
Mo 15: 2.5	Mo 15: 3.25	Mo 15: 23%	Mo 15: 6.2	15-mo intervals: 0.780
Mo 18: 2.5	Mo 18: 3.25	Mo 18: 24%	Mo 18: 6.2	

Power Calculations Scenario 1:				
N per arm at baseline	N per arm at 18 mo	Estimated Statistical Power	95% Lower Bound of Statistical Power	95% Upper Bound of Statistical Power
75	57	82.3%	79.8%	84.6%
70	53	78.6%	75.9%	81.1%
65	49	76.3%	73.5%	78.9%

Power Calculations Scenario 2:				
N per arm at baseline	N per arm at 18 mo	Estimated Statistical Power	95% Lower Bound of Statistical Power	95% Upper Bound of Statistical Power
75	57	95.6%	94.1%	96.8%
70	53	92.6%	90.8%	94.2%
65	49	91.8%	89.9%	93.4%

[figure not shown]
Note that with the given m-ITT design, the linear mixed effects model will actually include data from all subjects who have at least a baseline and one follow-up measure of FVC %. In this setting, even with an overall 24% attrition by the end of 18 months, it is estimated that 83% of the maximal possible study outcome data points (assuming no attrition) would be included in the analysis.

According to Scenario 1, which is strictly based on the documented capacity for PFD to slow the rate of decline of lung function in patients with IPF who are not receiving any other treatment, a sample size of 75 patients per treatment arm is required to obtain a minimum power of 80% (i.e., 80% is within the 95% CI for this prediction). If PFD has novel effects when combined with MMF so that it both reduces the rate of lung decline and works in concert with MMF to improve overall lung function (i.e., Scenario 2), then the predicted outcome will be much more reliably detected and a smaller sample size would be sufficient.

Having established adequate estimates of study power in a population of treatment naïve patients, the clinical trial Scenarios were then adjusted to assess the impact of a mixed starting population of patients in which some of the participants are treatment naïve and others have been on prior treatment with MMF (or DMARD with similar activity) for a period of 3, 6 or 9 months. Additional assumptions associated with these modified Scenarios include:

- 1) The mean change in FVC-% over a given 3-month interval and the corresponding impact on the standard deviation of the FVC-% measurement will always reflect the total time that a patient has been on therapy, including therapy that was administered before randomization and therapy that was administered following randomization.
- 2) The treatment effect is measured as the change from baseline, in which baseline is determined at the time of randomization (baseline visit). The baseline FVC-% measurement therefore establishes the zero reference value for evaluating change over time in response to the time that a patient is on the protocol. In this setting, patients who have been on 3 months or more of MMF will not be expected to experience the initial decline in lung function that occurs when enrolling treatment naïve patients.
- 3) As one of the hypothesized benefits of starting PFD and MMF at the same time in treatment naïve patients is the prevention of an early decline in lung function, there is a relative treatment penalty in the predicted PFD+MMF arm when patients have been on prior therapy with MMF. This results in less and less separation between the course of the two treatment arms as the length of time on prior MMF increases. This impact must be accounted for when modeling treatment outcomes and predicting study power.

**Figure 7.2. Hypothesized Response Trajectories over the 18-Month Double-Blind Treatment Period by Treatment Group for Scenario 2 based on length of time on MMF therapy prior to randomization.**

The power to detect a response according to Scenario 2, when taking into account the length of prior treatment with MMF (naïve, 3 mo, 6 mo and 9 mo strata) and the percentage of subjects within each of these strata, was then calculated by carrying out 1,000 clinical trials simulations for each situation in SAS 9.4 as already described. We varied the proportion of patients from 100% naïve down to 50% naïve, with the distribution across the prior treatment with MMF strata varied as described below. Estimates of the differences between treatment arms and the standard deviation for the measurements at a given time were adjusted according to the scenario curves shown in Figure 7.2.

**Table 7.2.** Power to detect differences in the response pattern from baseline to 18 months for the primary outcome (change in FVC-%) when comparing the course of change in lung function over time for the MMF+PFD arm and the MMF+Plac arm according to Scenario 2 with different mixtures of treatment naïve patients and those who were on prior MMF therapy for 3, 6 or 9 months as indicated. Results assume a 5% two-sided type I error and are provided for three different sample sizes (N = 75/arm; 70/arm and 65/arm)

a. Scenario 2: N = 75 per arm

% per stratum (length of prior MMF)				Estimated statistical power based on 1000 clinical trial outcome simulations		
Naive	3 mo	6 mo	9 mo	Power	95% Lower Bound	95% Upper Bound
1.00	0.00			95.6%	94.1%	96.8%

0.80	0.20			93.8%	92.1%	95.2%
0.75	0.25			92.2%	90.4%	93.8%
0.70	0.30			90.8%	88.8%	92.5%
0.60	0.40			90.5%	88.5%	92.2%
0.50	0.50			86.1%	83.8%	88.2%
0.80	0.10	0.10		91.4%	89.5%	93.1%
0.70	0.20	0.10		89.5%	87.4%	91.3%
0.70	0.10	0.20		90.2%	88.2%	92.0%
0.60	0.30	0.10		89.0%	86.9%	90.9%
0.60	0.20	0.20		88.2%	86.0%	90.1%
0.60	0.10	0.30		85.2%	82.8%	87.3%
0.50	0.40	0.10		84.7%	82.3%	86.9%
0.50	0.30	0.20		82.7%	80.2%	85.0%
0.50	0.20	0.30		82.7%	80.2%	85.0%
0.50	0.10	0.40		79.7%	77.1%	82.2%
0.70	0.10	0.10	0.10	86.4%	84.1%	88.5%
0.60	0.20	0.10	0.10	86.2%	83.9%	88.3%
0.60	0.10	0.20	0.10	83.7%	81.3%	85.9%
0.50	0.30	0.10	0.10	79.9%	77.3%	82.3%
0.50	0.20	0.20	0.10	79.3%	76.7%	81.8%

b. Scenario 2: N = 70 per arm

% per stratum (length of prior MMF)				Estimated statistical power based on 1000 clinical trial outcome simulations		
Naive	3 mo	6 mo	9 mo	Power	95% Lower Bound	95% Upper Bound
1.00	0.00			91.8%	89.9%	93.4%
0.80	0.20			91.3%	89.4%	93.0%
0.70	0.30			88.1%	85.9%	90.0%
0.60	0.40			86.0%	83.7%	88.1%
0.50	0.50			84.6%	82.2%	86.8%
0.80	0.10	0.10		89.4%	87.3%	91.2%
0.70	0.20	0.10		88.7%	86.6%	90.6%
0.70	0.10	0.20		85.6%	83.3%	87.7%
0.60	0.30	0.10		85.7%	83.4%	87.8%
0.60	0.20	0.20		82.9%	80.4%	85.2%
0.60	0.10	0.30		81.5%	79.0%	83.9%
0.50	0.40	0.10		83.0%	80.5%	85.3%
0.50	0.30	0.20		81.5%	79.0%	83.9%

0.50	0.20	0.30		79.9%	77.3%	82.3%
0.50	0.10	0.40		79.9%	77.3%	82.3%

c. Scenario 2: N = 65 per arm

% per stratum (length of prior MMF)				Estimated statistical power based on 1000 clinical trial outcome simulations		
Naive	3 mo	6 mo	9 mo	Power	95% Lower Bound	95% Upper Bound
1.00	0.00			91.8%	89.9%	93.4%
0.80	0.20			88.2%	86.0%	90.1%
0.70	0.30			85.5%	83.2%	87.6%
0.60	0.40			81.4%	78.9%	83.8%
0.50	0.50			79.7%	77.1%	82.2%
0.80	0.10	0.10		87.1%	84.9%	89.1%
0.70	0.20	0.10		85.5%	83.2%	87.6%
0.70	0.10	0.20		83.2%	80.7%	85.5%
0.60	0.30	0.10		78.4%	75.7%	80.9%
0.60	0.20	0.20		77.5%	74.8%	80.0%

According to these predictions for Clinical Trial Scenario 2, representing the primary outcome to be investigated, the study is adequately powered (80% power or greater) to detect a difference between the two treatment arms when the sample size is 150 and the patient population contains at least 50% treatment naïve patients. If the remaining 50% of enrolled patients are limited to no more than 6 months of prior therapy with MMF, then adequate power is maintained across the entire range of anticipated distributions between subjects with up to 3 mo of prior therapy and those with between 3 to 6 mo of prior therapy.

As a result, the target study population will consist of at least 50% of patients who are treatment naïve and up to 50% of patients who recently started on therapy within 6 months of entering the study (as detailed in Table 7.2 above). With this mixture of patients, the power remains adequate even if only 70 patients are enrolled in each arm (total randomization 140 patients), providing optimal flexibility for the enrollment phase of the study.

When a similar statistical approach is applied to Clinical Trial Scenario 1, in which only a small additive effect of PFD is modeled in addition the underlying treatment response to MMF, the power to detect a difference between the two treatment arms is adequate (80% power or greater) when the sample size is 150 and the patient population contains at least 75% treatment naïve patients. When the percentage of treatment naïve patients is reduced to 50%, the predicted power is at best 75% (assumes % per stratum of 50% naïve, 40% 3 mo, 10% 6 mo).

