## 4 Introduction

### 4.1 Preface

This Statistical Analysis Plan (SAP) describes statistical methods and analyses for the SLS III (Scleroderma Lung Study III) trial. This document should be read in tandem with the SLS III Study Protocol version 2.5, dated November 17, 2021.

Scleroderma Lung Study III proposes to investigate a new combination therapy for patients with SSc-ILD that will combine the established effects of immunosuppression, as mediated by MMF, with the anti-fibrotic effects of PFD. The primary hypothesis is that the rapid onset and anti-fibrotic activity of PFD, which have been observed in the treatment of IPF, will complement the delayed anti-inflammatory and immunosuppressive effects of MMF, to produce a significantly more rapid and/or greater improvement in lung function over time than occurs in patients receiving control therapy with MMF (and Plac) alone. A secondary objective is to demonstrate that combination therapy with PFD and MMF is well tolerated, in comparison to MMF alone, and not associated with limiting toxicity that impacts on the overall treatment effect.

The SLS III study is designed as a Phase II multi-center, double-blind, parallel group, randomized and placebo-controlled clinical trial addressing the treatment of patients with active and symptomatic SSc-ILD. Participants were randomized in a 1:1 assignment to receive either oral MMF and Plac (acting as a control arm) or a combination of oral MMF and oral PFD (acting as an experimental arm), with both regimens administered for 18 months. The length of therapy, 18 months, was established based on prior studies with immunosuppressive therapy alone, which demonstrated that 18 months represents the time required to achieve a peak treatment response. The primary outcome will include physiologic measures of lung function, HRCT imaging measures of lung inflammatory and fibrotic changes, dyspnea, assessments of skin inflammation and thickening, and patient reported measures of symptoms and quality of life. Tolerability and toxicity of the two treatments will also be assessed.

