**c. Additional Other Endpoints**

Because we had to stop enrollment before the planned sample size was achieved, we changed the classification of "other important endpoints" to "other endpoints"; modified the classification of PROMIS-19 endpoints to "other"; and added or clarified the additional other endpoints: categorized QILD-WL and two FVC-% endpoints based on the meaningful clinical importance difference; remove frequency distribution of DLCOHb-% because it is the most variable of the PFTs, and changed LCQ to the supplemental questions in LCQ. These changes clarify the importance of interpreting endpoints in the context of the reduced sample size.

PROTOCOL:

Section 4.2.2 Secondary Endpoints

4.2.2.4 The change from baseline to 18 months, measured at 3-month or 6-month intervals, in Patient Reported Outcomes (PROs), which provide subjective measures of dyspnea and quality of life based on patient responses to standardized patient questionnaires which include:

- c) Patient-reported outcomes measurement information system 29-item health profile (PROMIS-29 version 2.0); 6 month intervals

4.2.2.6 Differences in the frequency distribution of individual patient responses when grouped into defined intervals of improvement or worsening (defined by the change in an outcome measure from baseline to 18 months) for the following outcome measures:

- b) Single-breath diffusing capacity for carbon monoxide (DLCO), calculated as a percent of the age, height, gender-, race- and hemoglobin-adjusted predicted value (DLCOHb-%).

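### SAP 7 gives power only for 65 to 75 per arm and calls it adequate down to 140 patients, while the primary model is indexed over 51, where the plan's own figures imply roughly 37% to 57%

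*SAP*

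**What the plan says.** SAP 7 starts from "An initial sample size target of 150 participants (up to 190 consented and screened subjects to achieve 75 randomized per treatment group"), with two effect scenarios. In Scenario 1, "The collective result is a 2.5% greater response to treatment at 12 months in the experimental versus control arms" and the gap then stays constant. In Scenario 2 the gap is 3.125 points at 12 months and "continues to slowly increase to a final 3.25% difference between the two groups at 18 months".

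Table 7.1 gives power for an all-naive population at 75, 70 and 65 per arm: 82.3%, 78.6% and 76.3% in Scenario 1; 95.6%, 92.6% and 91.8% in Scenario 2. Table 7.2 repeats Scenario 2 for mixtures of naive and MMF-treated patients at the same three sizes. The section then concludes, for a population with at least half naive and the rest on no more than 6 months of prior MMF: "With this mixture of patients, the power remains adequate even if only 70 patients are enrolled in each arm (total randomization 140 patients"). For Scenario 1 at 50% naive it concedes at best 75%.

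Elsewhere in the same SAP, the primary model (10.1) runs over patients i = 1 to 51, and 10.1 assigns that analysis to the m-ITT set. Section 14, item c, opens "Because we had to stop enrollment before the planned sample size was achieved", and items g and i give the same reason.

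**The concern.** SAP 7 is operative text in the document that governs the analysis. It was issued by authors who already knew that recruitment had fallen short, yet nothing in it marks the power tables as superseded. Section 14 uses the reduced sample to drop or downgrade endpoints and analyses, but gives no revised power, detectable difference or expected precision for the primary test.

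What is at stake is how the primary result will be read. If it is non-significant, the only power statement on record runs from about 75% to 96%, and a reader could take the result as evidence that adding pirfenidone does little. With 51 patients, a non-significant result would be about as likely as not, or likelier, even if the planned benefit were real.

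**Working it through.** **Inputs.** From SAP 7 and Table 7.1:
- "A 5% two-sided type I error is assumed"; allocation 1:1 (SAP 4.1).
- Differences at months 3 to 18: Scenario 1, 0.5, 1.375, 2.25, 2.5, 2.5, 2.5; Scenario 2, 0.75, 1.75, 3.0, 3.125, 3.25, 3.25.
- SDs 4.1, 5.1, 6.2, 6.9, 6.2, 6.2; correlations by lag 0.866, 0.834, 0.802, 0.790, 0.780.
- Cumulative dropout 6.5, 13, 17, 20, 23, 24%.

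From SAP 10.1: 51 patients. Assumed, because no split is given: 25.5 per arm (26 and 25 in simulation).

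**Reproducing the plan.** Trials were simulated from these inputs (6,000 per cell) and fitted with a compound-symmetry mixed model, month as a category. The baseline covariate was left out because its correlation with change is not given. The 5-df treatment-by-month F-test gives 81.8%, 78.8% and 75.8% for Scenario 1 (stated 82.3, 78.6, 76.3) and 95.2%, 93.8% and 91.7% for Scenario 2 (stated 95.6, 92.6, 91.8). All six agree within 2 points. A test of the 18-month average gives 57.6% and 79.0% at 75 per arm, so it is not the test behind the stated powers.

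**Scaling to 51.** Power = Φ[(1.96 + z_power) × √(25.5/75) − 1.96], with √(25.5/75) = 0.583.

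| Row at 75 per arm | Stated power | 1.96 + z_power | × 0.583 | Power at 51 |
|---|---|---|---|---|
| Scenario 1, all naive | 82.3% | 2.887 | 1.683 | 39% |
| Scenario 2, all naive | 95.6% | 3.666 | 2.138 | 57% |
| Scenario 2, 50% naive, 50% 3 mo | 86.1% | 3.045 | 1.775 | 43% |
| Scenario 2, 50% naive, 10% 3 mo, 40% 6 mo | 79.7% | 2.791 | 1.627 | 37% |
| Scenario 1, 50% naive (best case) | 75% | 2.634 | 1.536 | 34% |

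This is a 1-df approximation to a 5-df test. Simulating the reproduced test directly with 26 and 25 patients gives 37.7% (Scenario 1) and 52.9% (Scenario 2), all naive.

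**Sensitivity to the form of the test.** SAP 10.1 specifies an unstructured covariance, whereas the power simulations used compound symmetry. An approximate F calculation of the interaction test with unstructured covariance gives about 25% and 39% at 51. If month is a linear term under compound symmetry, simulation gives about 53% and 67% at 51, but that version gives 88% for Scenario 1 at 75 per arm and so does not reproduce the stated 82.3%. Under no effect, the reproduced compound-symmetry test rejected in about 6.9% of simulations, so the plan's powers are somewhat flattering.

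**Separate calculation: mean change over 18 months.** The planned average differences are 11.625/6 = 1.94 and 15.125/6 = 2.52. Generalised least squares with the stated SDs, correlations and dropout gives a variance of 31.50 per randomised patient for the six-visit mean. Then SE = √(2 × 31.50/25.5) = 1.572, the 95% CI half-width is 1.96 × 1.572 = 3.08 points, and power is about 23% and 36%. If baseline FVC-% explained an assumed 10% to 30% of the variance, the half-width would be 3.08 × √0.9 = 2.9 to 3.08 × √0.7 = 2.6, and power about 25% to 31% and 39% to 48%.

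**The case against.** The best defence is that Section 7 is visibly planning text. It opens with "An initial sample size target of 150 participants", follows protocol 10.5, and its adequacy sentence is conditional on enrolling 70 per arm. It does not claim power for the sample analysed. Section 14 does mention interpretation in light of the reduced size, and SAP 10.1 already calls for a 95% CI on the treatment difference. No estimand, model or alpha changes. This limits the remedy to wording, but does not remove the gap: the only power on record is for a trial at least two and a half times the size of the one analysed (130/51 = 2.5), and no text connects the two.

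Three stronger readings are tempting and should be resisted.

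- A reader might infer that enrolment stopped at 51. The documents give 51 only as the index of an m-ITT model, and m-ITT requires a post-baseline assessment. If the planned 6.5% month-3 loss is already removed, 51 corresponds to 51/0.935 = 54.5 randomised, and the scaled all-naive powers become about 41% and 60%. The conclusion is unchanged.
- A reader might infer that a significant result could only come from an estimate at least as large as the planned effect. That is not generally so: at the scaled 57%, the threshold is 1.96/2.138 = 92% of the planned effect.
- A reader might infer that the shortfall was applied only to secondary endpoints. Section 14, item g, removes the change-point analysis of the primary endpoint for this reason.

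The all-naive 57% is also not the closest match to the adequacy sentence, which allows as few as 50% naive patients; at that floor the comparable range is 37% to 43%.

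**Conclusion.** The point holds. SAP 7 describes power that the trial in SAP 10.1 does not have. Under the plan's own assumptions, with about 25.5 per arm and all patients naive, power is about 39% by scaling (38% by simulation) in Scenario 1 and 57% (53%) in Scenario 2. At the 50% naive floor, Scenario 2 scales to about 37% to 43%. The other forms of test examined move these figures, but none reaches 80%. For mean change, the expected half-width of about 3.1 points before baseline adjustment exceeds both planned average differences.

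These figures rest on 51 being the analysed number, a near-equal split, and the planned SDs, correlations and dropout. The actual stratum mix and the gain from baseline adjustment are not in the documents.

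**What to change.** In SAP 7, label the 65 to 75 per arm tables and the adequacy sentence as original planning that no longer describes this trial. Add, at the actual sample size and stratum mix and under the stated primary test, the power for Scenarios 1 and 2 and the expected 95% CI half-width. State the number randomised and the arm split if this can be done without compromising the blind. Before unblinding, state that a non-significant primary result will be treated as inconclusive unless the 95% CI excludes the planned differences.

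This changes SAP wording only; no endpoint, model or trial procedure is affected. The cost is a much less favourable stated power. SAP 8.1 places finalisation before database lock and unblinding, and the interpretive rule carries weight only if it is written by then.
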